# 13.0 Data management guidelines

## 13.1 Case report forms and data entry

All participant data collected will be entered onto paper case report forms (CRFs) prior to entry onto a secure data entry system. The Site PI will oversee and be responsible for data collection, quality and recording. Collection of data can be delegated by the Site PI to qualified members of the research team and should be recorded on the Delegation of Trial Duties Log.

Data collected during the course of SCARF will not be anonymised in order to allow participants to be traced for outcome data. This is detailed in the PIS and on the Consent Form.

During the conduct of the trial, all electronic participant data will be encrypted and all trial documents stored securely at the site or the ICNARC CTU, as appropriate. On completion of the trial, all participant data (electronic and paper) and other trial documents will be archived securely and retained for ten years at the site or at the ICNARC CTU, as appropriate (see section 17.0).

ICNARC is registered under the Data Protection Act 1998 and all ICNARC CTU staff have undergone data protection and International Conference on Harmonisation (ICH) Good Clinical Practice (GCP) training.

## 13.2 Data validation

Data entered onto the secure trial database will undergo validation checks for completeness, accuracy and consistency of data. Queries on incomplete, inaccurate or inconsistent data will be sent to the research team at participating sites for resolution.

#### 14.0 Adverse events

The following definitions have been adapted from Directive 2001/20/EC, of 4 April 2001, of the European Parliament (Clinical Trials Directive) and ICH GCP E6 guidelines:

#### 14.1 Adverse event

An adverse event (AE) is defined as any untoward medical occurrence or effect in a participant treated on a trial protocol, which does not necessarily have a causal

relationship with trial treatment. An AE can therefore be any unfavourable symptom or disease temporally associated with the use of the trial treatment, whether or not it is related to the trial treatment.

#### 14.2 Serious adverse event

A serious adverse event (SAE) is defined as an AE that:

- results in death;
- is life threatening (the term "life-threatening" refers to an event in which the subject was at risk of death at the time of the event. It does not refer to an event that hypothetically might have caused death if it were more severe);
- requires in-patient hospitalisation or prolongs existing hospitalisation;
- results in persistent or significant disability/incapacity;
- consists of a congenital anomaly or birth defect.

## 14.3 Recording and reporting procedures

All infants and children eligible for SCARF are critically ill and due to the complexity of their condition are at increased risk of experiencing AEs. Many of these events are expected as a result of the infant/child's medical condition and standard treatment received in the PICU, but may not be related to participation in the trial. Consequently, any AEs occurring as a result of the infant/child's medical condition or standard critical care treatment will not be reported. Pre-existing conditions do not qualify as AEs unless they worsen, but should be documented in the infant/child's medical notes.

All other AEs that occur between randomisation and 30 days post-randomisation must be recorded in the participant's medical notes and on the SCARF CRF. Information regarding date and time of event onset, severity and relatedness of the AE to trial treatment must be recorded (definitions below).

Those meeting the definition of a SAE (i.e. severity 3, 4 or 5 – see section 14.4) must, in addition, be recorded in the SAE Log and reported to the ICNARC CTU, using the trial specific SCARF SAE Reporting Form, by fax within **24 hours** of observing or learning of the SAE. All sections of the SAE Reporting Form must be completed.

The process for recording and reporting AEs and SAEs is summarised in Figure 2.

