#### 14.4 Severity

The Site PI, or other delegated investigator(s) (recorded in the Delegation of Trial Duties Log), must perform an assessment of severity for each AE using the following criteria:

- 0. **None**: indicates no event or complication.
- 1. **Mild**: complication results in only temporary harm and does not require clinical treatment.
- 2. **Moderate**: complication requires clinical treatment but does not result in significant prolongation of hospital stay. Does not usually result in permanent harm and where this does occur the harm does not cause functional limitation to the participant.
- 3. **Severe**: complication requires clinical treatment and results in significant prolongation of hospital stay, permanent functional limitation.
- 4. Life-threatening: complication that may lead to death.

5. **Fatal**: indicates that the participant died as a direct result of the complication/adverse event.

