## **13. Safety**

The number and percentage of Serious Adverse Events (SAEs) within 30 days (either from admission to PICU for early delivery of CPAP or from randomisation for children and infants randomised to standard care) will be reported. SAEs will be compared between treatment groups using Fisher's exact test.

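### Protocol 14.3 makes SAE reporting depend on open-label attribution and equates 'serious' with severity 3 to 5, against 14.2; the SAE comparison may be distorted, in a direction and by an amount that cannot be established

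*Protocol*

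**What the plan says.** **Exemption.** Protocol 14.3 notes that many events are expected from the child's "medical condition and standard treatment received in the PICU, but may not be related to participation in the trial". It concludes that those arising from the child's illness "or standard critical care treatment will not be reported". All other adverse events from randomisation to 30 days go in the notes and on the CRF. The critical-care term is not defined.

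**Seriousness.** The same section sends for expedited reporting "Those meeting the definition of a SAE (i.e. severity 3, 4 or 5" on the scale in 14.4). Section 14.2 has its own list, which includes an event that "requires in-patient hospitalisation or prolongs existing hospitalisation". Grade 2 in section 14.4 is described as: "complication requires clinical treatment but does not result in significant prolongation of hospital stay".

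**Use of the data.** Protocol 18.4 has the DMEC monitor safety through mandatory SAE reports. SAP 13 says "SAEs will be compared between treatment groups using" Fisher's exact test. It counts events from PICU admission in the CPAP arm and from randomisation in the control arm.

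**The concern.** Section 14.1 defines an adverse event without regard to cause. Section 14.3 then removes events by cause, and one of the exempt causes is the kind of care to which one arm is allocated: Protocol 10.1 makes PICU admission part of the intervention. Protocol 7 of the trial's rationale is not needed to see the difficulty, because a line, sedation or unit-acquired infection event in a CPAP-arm child could be read either as a consequence of the allocated strategy or as ordinary critical care. Site staff decide which, knowing the allocation, and the documents describe no blinded or independent check of that decision.

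The SAE rule adds a second problem. It presents two different definitions as equivalent, so sites could report different sets of events depending on which they follow.

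At stake is what the SAE comparison can support. A finding of no excess could partly reflect the filter, and so could a finding of excess. The DMEC relied on the same reports, and SAP 12 says that the planned interim analysis was not carried out.

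**Working it through.** **1. Does the exemption operate in both arms?** Protocol 10.2 allows control children to be admitted to PICU when needed. Protocol 19.1 gives a rough idea of how often.

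- PICU admissions with severely impaired immunity: 3.3 per month, two thirds for respiratory failure: 3.3 × 2/3 = 2.2.
- Ventilated: 75% of these: 2.2 × 0.75 = 1.65.
- Similar children who stay on the ward: about 2.2, so the eligible total is 2.2 + 2.2 = 4.4 per month. This agrees with the plan's 4 to 5.
- Implied control intubation rate: 1.65 / 4.4 = 37.5%. This agrees with the plan's 35 to 40%.
- Implied share reaching PICU under usual care: 2.2 / 4.4 = 50%.

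So all CPAP-arm children are meant to enter PICU, against about half of controls. Exposure to exemptible care is unequal, but it is not confined to one arm.

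**2. Do later provisions recover exempted events?** No. Section 14.9 monitors adverse events that were documented, and central review under 14.8 starts when an SAE report arrives. Appendix 1 refers events back to section 14.0, which contains the exemption.

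**3. Do 14.2 and the severity rule agree?**

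| Event | Under 14.2 | Under 14.4 | Under "i.e. severity 3, 4 or 5" |
|---|---|---|---|
| Treated; lengthens stay, but not significantly | Serious (any prolongation) | Grade 2 | Not an SAE |
| Could prove fatal, but no risk of death at the time | Not life-threatening (hypothetical risk excluded) | Grade 4 | SAE |
| Leads to death, but not directly | Serious (no directness condition) | Not grade 5; possibly grade 4 | Depends on grading |

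The rule is narrower than 14.2 in one place and wider in another. It is the same in both arms, so it misclassifies events without giving a direction of its own.

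**4. What could the filter do to the comparison?** The documents give neither SAE rates nor exempted shares, so everything in this step is assumed. Let eI and eC be the shares of SAEs exempted in the CPAP and control arms. Then:

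reported RR = true RR × (1 − eI) / (1 − eC)

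*Equal true risks (true RR = 1).* With shares from 0 to 60%, the extremes are 0.4 / 1 = 0.40 and 1 / 0.4 = 2.50. The next table takes a true risk of 20% in each arm and the planned 74 per arm. Rejection probabilities are from exact enumeration of Fisher's test at two-sided 0.05.

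| eI | eC | Reported CPAP v control | RR | Significant result |
|---|---|---|---|---|
| 20% | 20% | 16% v 16% | 1.00 | 2.9% (both directions together) |
| 60% | 20% | 8% v 16% | 0.50 | 24.4%, favouring CPAP |
| 20% | 60% | 16% v 8% | 2.00 | 24.4%, against CPAP |

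*A true excess of 30% v 15% (true RR = 2.0), again with 74 per arm.*

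| eI | eC | Reported CPAP v control | RR | Power to show harm |
|---|---|---|---|---|
| 0 | 0 | 30% v 15% | 2.0 | 51.9% |
| 30% | 30% | 21% v 10.5% | 2.0 | 33.6% |
| 50% | 0 | 15% v 15% | 1.0 | 1.5% |
| 0 | 50% | 30% v 7.5% | 4.0 | 93.2% |

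Equal filtering leaves the relative risk intact but costs power. Unequal filtering can hide a difference, create one or exaggerate one. The relative risks do not depend on sample size. The probabilities apply only to the planned size, and SAP 12 implies that fewer than 148 / 2 = 74 children were recruited in total.

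**The case against.** A reader might infer that harms of the PICU strategy simply go unreported and that the comparison is biased towards CPAP. The documents do not support that, for four reasons.

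- Controls do receive critical care (step 1), so the exemption applies to them too. If early CPAP works as hypothesised, controls would have more invasive ventilation, with complications that can be exempted.
- In the CPAP arm, PICU admission with CPAP is the trial treatment, so its complications can be read as reportable. The same complication in an escalated control child could be put down to standard care. That would bias against CPAP.
- Appendix 1 names pneumothorax, facial pressure sores, aspiration and similar events as adverse events to be recorded and reported.
- Death and intubation are collected as outcomes whatever their cause.

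These points defeat any claim about direction, and 'may go unreported' is as far as the text goes. Figure 2, which summarises the reporting process, is not available for this review and might clarify the rule. The objection does not remove the defect itself: the term is undefined, both exemption clauses rest on unblinded attribution, and no later step sees an event that was never documented.

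It can also be said that SAP 9, 10.1 and 10.3 already analyse Level 4 support, mortality and PELOD without this filter. That is correct and makes the remedy cheap, but SAP 13 still presents the SAE test with no caveat.

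**Conclusion.** Two defects stand. First, SAE ascertainment depends on open-label attribution, in a trial where one exempt cause overlaps with the allocated strategy. Under-reporting may differ between arms; the greater planned PICU exposure in the CPAP arm makes that plausible but does not fix its direction. Second, the severity 3 to 5 rule contradicts 14.2. It is tempting to count this as further bias towards CPAP, but the rule is identical in both arms and errs both ways.

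No magnitude follows from the documents. The range of 0.40 to 2.50 shows only what assumed exempted shares of 0 to 60% could do when the true risks are equal. The figure of about half of controls reaching PICU rests on reading the similar number in Protocol 19.1 as similar to the respiratory-failure admissions, the reading that reproduces the plan's own accrual and intubation figures.

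The arm-specific start of the SAE window in SAP 13 conflicts with the common start in Protocol 14.3. It is a further asymmetry in the same test and needs no assumed rates to see.

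**What to change.** **Protocol 14.3, if events are still being collected.**

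- Replace "i.e. severity 3, 4 or 5" with: any event meeting section 14.2, whatever its severity grade.
- Record and report events meeting 14.2 in both arms, from randomisation, whatever their attributed cause. This must lift both exemptions for such events. Removing only the critical-care clause would leave the medical-condition clause, and reporting would still turn on attribution.
- Record the attributed cause as a separate field, so that it can be analysed rather than used as a filter.

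The cost is more SAE forms, in a population where serious events are common.

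**SAP 13, if data collection has closed.** This looks the likelier case: recruitment was planned to end in January 2016 and the SAP is dated 22/09/2016.

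- State that SAEs are investigator-attributed and filtered under Protocol 14.3.
- Do not read the Fisher P value as evidence of no excess harm.
- Base the safety conclusion on outcomes already analysed without the filter: all mortality endpoints, Level 4 support and PELOD.
- Start the SAE window at randomisation in both arms, as in Protocol 14.3.

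This costs a few sentences of SAP text and a small change to the window. It cannot recover events that were never recorded, and the unfiltered outcomes do not cover every type of harm.

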#### 14.4 Severity

The Site PI, or other delegated investigator(s) (recorded in the Delegation of Trial Duties Log), must perform an assessment of severity for each AE using the following criteria:

- 0. **None**: indicates no event or complication.
- 1. **Mild**: complication results in only temporary harm and does not require clinical treatment.
- 2. **Moderate**: complication requires clinical treatment but does not result in significant prolongation of hospital stay. Does not usually result in permanent harm and where this does occur the harm does not cause functional limitation to the participant.
- 3. **Severe**: complication requires clinical treatment and results in significant prolongation of hospital stay, permanent functional limitation.
- 4. Life-threatening: complication that may lead to death.

5. **Fatal**: indicates that the participant died as a direct result of the complication/adverse event.

#### 14.5 Relatedness

The Site PI or other delegated investigator(s) must perform an assessment of relatedness for each AE. This must be determined as follows:

#### None

There is no evidence of any relationship.

### Unlikely

There is little evidence to suggest a relationship (e.g. because the event did not occur within a reasonable time after administration of the trial treatment). There is another reasonable explanation of the event (e.g. the participant's clinical condition, other concomitant medications).

#### Possible

There is some evidence to suggest a relationship (e.g. because the event occurs within a reasonable time after administration of the trial procedure). However, the influence of other factors may have contributed to the event (e.g. the participant's clinical condition, other concomitant medications).

#### Probable

There is evidence to suggest a relationship and the influence of other factors is unlikely.

## Definitely

There is clear evidence to suggest a relationship and other possible contributing factors can be ruled out.

## 14.6 Expectedness

The Site PI or other delegated investigator(s) must perform an assessment of expectedness for each AE regardless of its relationship to the trial procedures. This assessment must be performed using the list of expected AEs in Appendix 1 and determined as follows:

#### Expected

The event is listed as an expected AE in Appendix 1, or is considered by a clinician to be an expected complication in this patient population (this would include rare complications).

#### Unexpected

The event is not listed as an expected AE in Appendix 1, or is considered by a clinician to be an unexpected event.

#### 14.7 Follow-up of serious adverse events

All SAEs must be followed-up until resolution. The Site PI or other delegated investigator(s) must provide follow-up SAE report(s) if the SAE has not been resolved at the time of the initial report submission.

#### 14.8 Central processing of serious adverse event reports

On receipt of the SAE report, a clinical member of the SCARF Trial Management Group (TMG) will evaluate the event for severity, relatedness and expectedness to determine whether or not the case qualifies for expedited reporting to the Research Ethics Committee (REC).

If the event is evaluated by either the Chief Investigator or a clinical member of the SCARF TMG as a related and unexpected SAE, the ICNARC CTU will submit a report to the REC within 15 calendar days.

The ICNARC CTU will provide safety information to the Chief Investigator, TMG, Trial Steering Committee (TSC) and Data Monitoring and Ethics Committee (DMEC) for review on a regular basis (as deemed necessary).

[figure not shown]
## 14.9 Additional safety monitoring

The ICNARC CTU will also monitor data for documented AEs that are not considered to be related to the trial treatment. In the event that any trial procedure does appear to be resulting in AEs, the TMG will be contacted for their opinion. If it is declared necessary to review the conduct of the trial, the ICNARC CTU will inform the REC as appropriate.

## 14.10 Notifying the Research Ethics Committee

AEs that do not require expedited reporting will be reported in the annual progress report which will be submitted by the ICNARC CTU to the REC annually. This will commence one year from the date of approval for the trial.

Figure 2 Adverse event recording and reporting

# 15.0 Trial monitoring and oversight

The ICNARC CTU will conduct at least one monitoring visit to participating sites during the course of the trial. In addition, the REC may request access to source data/documents for audit and review. Trial participants and their parents will be informed of this during the informed consent process (see section 8.0).

Following a routine monitoring visit, a report will be sent, which will summarise the visit and the documents reviewed, along with any findings. The Site PI will be responsible for ensuring that all findings are addressed appropriately.

Additional site monitoring visits may be scheduled where there is evidence or suspicion of non-compliance with the SCARF Protocol.

## 16.0 Withdrawal

## 16.1 Withdrawal of a participant

In consenting/agreeing to the trial, parents/guardians and their children are consenting/agreeing to trial treatment, assessments, follow-up and data collection. However, children or their parents can withdraw from SCARF at anytime during the trial. If a child, or their parents, explicitly state that they no longer wish to take part or to contribute further data to the trial, their decision must be respected. The Withdrawal of Consent form should be completed and sent to the ICNARC CTU. Withdrawal of an infant or child from the trial should be recorded in their medical notes and no further data collected. To ensure the scientific validity of the trial and the safety of other participants, all data collected up to the point of withdrawal will be retained and primary outcome data (requirement for intubation and invasive mechanical ventilation within 30 days of randomisation) collected and included in the trial analysis. All identifiers will be removed at the end of the trial to ensure anonymity for all infants and children recruited into SCARF.

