## 19.0 Statistics

#### 19.1 Sample size calculation

Data submissions to the Paediatric Intensive Care Audit Network, the national clinical audit for PICUs in the UK, report a mean of 3.3 patients per month with severely impaired immunity admitted to GOSH PICU over the last eight years. Two thirds were admitted with respiratory failure as the primary reason for admission and 75% of these received mechanical ventilation. We estimate that a similar number experience acute respiratory distress on the ward fitting our inclusion criteria that do not require ICU admission. Therefore we would be expecting to randomise around 4-5 participants per month and anticipate an intubation rate of around 35-40% in the control group. Assuming the same relative risk reduction (~60%) as observed in adult studies, a sample of 148 children (74 in each group) is required to detect a reduction in intubation rate from 35% to 14% with 80% power and a type 1 error rate of 5% (two-sided).

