#### **6. Analysis principles**

All analyses will be conducted by intention to treat. The patients will be analysed according to the treatment group they were randomised to, irrespective of whether the treatment allocated was received i.e. all patients will be included in the analysis, regardless of whether they have, or have not, adhered to the protocol. A two-sided p value of <0.05 will be taken to indicate a statistically significant result.

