#### **7. Handling of missing data**

As the amount of missing data is anticipated to be minimal, a sensitivity approach will be taken when the primary outcome variable is missing. The primary analysis will be repeated once assuming that all patients allocated to early CPAP with missing outcomes did not receive invasive mechanical ventilation (Level 4 respiratory support), and all patients allocated to standard treatment with missing outcomes did receive invasive mechanical ventilation (Level 4 respiratory support). The analysis will then be repeated again with the opposite assumptions. This will then give the absolute range of how much the results could change if the primary outcome variable were complete.

In adjusted analyses missing baseline data will be handled by multiple imputation using chained equations.

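### Protocol 16.1 has one withdrawal route that ends everything but the primary outcome, so mortality and SAE data that could be kept are lost, and the SAP has no rule for missing mortality

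*Protocol*

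**What the plan says.** **Withdrawal.** Protocol 16.1 is triggered when a child or parent explicitly states one of two wishes: not to take part any longer, or not to contribute further data. Both lead to one form and one consequence: "Withdrawal of an infant or child from the trial should be recorded in their medical notes and no further data collected". The next sentence adds that "all data collected up to the point of withdrawal will be retained and primary outcome data" will be collected and analysed. No status is described for leaving trial treatment or active participation while staying in follow-up.

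**Safety.** Protocol 14.7: "All SAEs must be followed-up until resolution". It makes no provision for withdrawn children.

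**Survival.** Improved survival is in the aim (Protocol 3.0) and in the SAP's primary objective (SAP 2). After discharge, mortality at 30 days, 90 days and one year comes from flagging with the hospital system and the national data linkage service (Protocol 12.0). The consent form described in Protocol 8.0 covers access to those records.

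**Analysis.** SAP 6: "all patients will be included in the analysis, regardless of whether they have, or have not, adhered to the protocol". SAP 8.4 lists CPAP not received for the specified period as a protocol deviation. In SAP 7, "a sensitivity approach will be taken when the primary outcome variable is missing", using two opposite extreme assumptions; missing baseline data are multiply imputed. Nothing is said about missing mortality or any other missing secondary outcome.

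**The concern.** Two different wishes are merged. A parent who wants the child out of the trial, but has no objection to survival being read from routine records, is handled like a parent who refuses all further data. For the first family the loss of follow-up is avoidable.

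The loss falls on outcomes that matter: SAEs, PELOD, days free from ventilator support and oxygen, and mortality at 30 days, hospital discharge, 90 days and one year. It also sits badly with the unqualified SAE rule in 14.7.

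Withdrawal need not be balanced or unrelated to prognosis. Allocation is known to everyone. Only the intervention arm has PICU admission and at least 12 hours of CPAP a day for at least four days (Protocol 10.1), and Protocol 2.0 acknowledges that giving CPAP to young children can be challenging. If children leave one arm because they are doing badly, an available-case comparison of mortality or SAEs is biased, and the SAP has no planned analysis that would show by how much.

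**Working it through.** **1. What continues after withdrawal under 16.1**

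| Data | After withdrawal | Other text |
|---|---|---|
| Intubation within 30 days | Collected (exception in 16.1) | SAP 7 bounds if missing |
| AEs and SAEs | Stop | 14.7: follow to resolution |
| PELOD, support-free and oxygen-free days | Stop | No missing-data rule |
| 30-day, hospital, 90-day and one-year mortality | Stop | Flagging available (12.0); no missing-data rule |

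**2. The plan's own sample size.** Protocol 19.1 states that "a sample of 148 children (74 in each group) is required". Inputs: 35% v 14%, two-sided 5%, 80% power. With pooled rate 0.245:

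- n = [1.96√(2×0.245×0.755) + 0.842√(0.35×0.65 + 0.14×0.86)]² / 0.21² = 64.7, so 65 per group.
- With continuity correction: n' = (n/4)[1 + √(1 + 4/(0.21n))]² = 73.9, so 74 per group and 148 in total.

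The figure reproduces, and it contains no allowance for withdrawal.

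**3. Size of trial for the illustration.** SAP 12 says the 50% point was not reached. Half of 148 is 74, so at most 73 children. I assume 36 CPAP and 37 control.

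**4. Mortality illustration (assumed inputs).** The documents give no withdrawal counts and no mortality for this population. Protocol 2.0 quotes case fatality for acute lung injury and ARDS of about 20% in children overall, approaching 50% with immunocompromise. I use 7 deaths per arm (7/36 = 19%) and 18 per arm (18/36 = 50%) as a range. If m CPAP-arm children die unobserved after withdrawal:

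observed RR = [(d − m)/(36 − m)] / (d/37)

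| m | d = 7 per arm | d = 18 per arm |
|---|---|---|
| 0 (true) | (7/36)/(7/37) = 1.03 | (18/36)/(18/37) = 1.03 |
| 1 | (6/35)/(7/37) = 0.91 | (17/35)/(18/37) = 1.00 |
| 2 | (5/34)/(7/37) = 0.78 | (16/34)/(18/37) = 0.97 |
| 3 | (4/33)/(7/37) = 0.64 | (15/33)/(18/37) = 0.93 |

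For 4/33 v 7/37 the standard error of log RR is √(1/4 − 1/33 + 1/7 − 1/37) = 0.579. The 95% interval is 0.64 × exp(±1.96 × 0.579) = 0.21 to 1.99.

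**5. Other directions, d = 7.** If the 3 withdrawn CPAP children survived, the observed RR is (7/33)/(7/37) = 1.12. If instead 3 control deaths were unobserved, it is (7/36)/(4/34) = 1.65.

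**6. What bounds would show.** Applying SAP 7's opposite assumptions to 4 observed deaths and 3 missing CPAP children gives (4/36)/(7/37) = 0.59 if all lived and (7/36)/(7/37) = 1.03 if all died. The range contains the true value; the available-case estimate alone gives no warning.

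**The case against.** Four readings go further than the documents allow.

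*A reader might infer that 16.1 cannot be obeyed, because it both stops collection and requires the primary outcome.* The second sentence reads naturally as a named exception to the first, and a site can follow it. What remains is a consent question: the exception also applies to a family that has refused further data, and Protocol 8.0 says participation can be withdrawn without consequence.

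*A reader might infer that stopping CPAP means leaving follow-up.* It does not. SAP 8.4 counts it as a deviation and SAP 6 keeps the child in the analysis. The gap is narrower: 16.1 does not name this status, so staff have no text telling them to offer it to a family asking to leave.

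*A reader might infer that follow-up is in fact lost selectively in the CPAP arm.* No withdrawal counts appear, overall or by arm, and the number may be zero. Control families disappointed at not getting early PICU admission could also withdraw. The direction of any bias is open.

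*A reader might infer bias in the intubation result.* That needs the primary outcome to be lost, which 16.1 prevents, and SAP 7 already bounds any that is missing.

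Some other points stand. SAP 6 is about adherence, not withdrawn consent, and 14.7 is a general rule, so neither contradicts 16.1 outright. The withdrawal form and the data-collection SOP are not available here and may distinguish levels. Timing also limits the remedy: the SAP is dated 22/09/2016 and recruitment was planned to end in January 2016.

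**Conclusion.** The point holds as a should-fix. Followed as written, 16.1 stops all data after withdrawal except the primary outcome, including survival that could be had from flagging already consented to, and the SAP has no handling for missing mortality. The loss could be unequal by arm; whether it was cannot be told from the documents.

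The size is conditional. With 3 unobserved CPAP-arm deaths among 36 v 37 children, a true mortality RR of 1.03 would appear as 0.64 at 7 deaths per arm, but as 0.93 at 18 per arm. These figures rest on assumed deaths, an assumed split, and all losses being deaths in one arm; other patterns move the estimate the other way. The interval at 0.64 (0.21 to 1.99) is wide, so the harm would be a misleading point estimate rather than a false claim of significance. The primary outcome is not affected if 16.1 is followed.

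**What to change.** **Protocol 16.1 and the withdrawal form.** Distinguish:

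- (a) stopping trial treatment or active participation: 30-day outcome data, SAE follow-up and routine-record survival to one year continue unless explicitly refused;
- (b) explicit refusal of further data: collection stops at that date.

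State whether the existing primary-outcome exception applies to (b), and reconcile this with the consent wording. It should not simply be deleted: that would create missing primary outcomes where there are now none.

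**SAP.**

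- Classify existing withdrawals by what was refused, and report them by arm and reason.
- Extend the SAP 7 opposite-assumption analyses to 30-day, 90-day and one-year mortality.
- Censor children whose families refused data at last known status in the Kaplan-Meier curves.

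**Cost.** A small amendment with ethics committee submission, and a few extra sensitivity analyses. No new follow-up procedure is needed, because flagging is already set up. If recruitment ended as planned in January 2016, the 30-day and 90-day windows had closed by the SAP date, so the protocol edit can protect only remaining one-year survival. The SAP changes therefore matter most.
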